2.2 Rationale for the study design

[figure not shown]
This is a phase II, multi-center, open-label, five-arm study to evaluate the efficacy and safety of oral ceritinib treatment for patients with ALK-positive NSCLC metastatic to the brain and/or to leptomeninges. Only patients whose tumors harbor ALK rearrangement will be enrolled in the study. The study will enroll approximately 160 patients globally.

Patient population

Patients with ALK-positive NSCLC and active metastases into the brain and/or to leptomeninges will be included in this study.

Patients without evidence of leptomeningeal carcinomatosis (LC) will be allocated into one of the following 4 arms taking into account the patient's history of prior therapy: prior radiation therapy (whole brain or stereotactic radiation therapy) to the brain (yes/no) and a prior treatment with an ALK inhibitor (ALKi) (yes/no). Prior ALK inhibitor is limited to treatment with crizotinib in Arms 1, 2, and 5. All patients will have evaluable brain metastases following RECIST 1.1 as per investigator assessment.

The allocation of patients to arm 5 will be independent from the patient's history of prior therapy but rather depend on the presence of neoplastic cells in the cerebrospinal fluid (CSF) as assessed and documented by the investigator at baseline. In the absence of neoplastic cells in the CSF, the allocation of patients to arm 5 will then depend on the diagnosis of typical

radiological leptomeningeal carcinomatosis on the baseline gadolinium-enhanced MRI of the brain (or the spine for suspected LC patients only) by an experienced neuroradiologist.

Table 2-1 Allocation into Study Arms based on prior radiation to brain (yes/no) and prior treatment with ALK inhibitor (yes/no)

	Prior Radiation to the brain: YES	Prior Radiation to the brain: NO
Prior treatment with a ALKi ¹ : YES	Arm 1	Arm 2
Prior treatment with a ALKi: NO	Arm 3	Arm 4
Leptomeningeal disease ¹	Arm 5	

¹Previous treatment with ALK inhibitors other than crizotinib is not allowed in Arms 1, 2 and 5.

The description of patients in each of the five study arms is as follows:

[figure not shown]
- Arm 1 will include patients with metastases in the brain without evidence of leptomeningeal carcinomatosis, previously treated with radiation to the brain and with prior exposure to an ALKi.
- Arm 2 will include patients with metastases in the brain without evidence of leptomeningeal carcinomatosis, previously untreated with radiation to the brain but with prior exposure to an ALKi.
- Arm 3 will include patients with metastases in the brain without evidence of leptomeningeal carcinomatosis, previously treated with radiation to the brain but with no prior exposure to an ALKi.
- Arm 4 will include patients with metastases in the brain without evidence of leptomeningeal carcinomatosis, previously untreated with radiation to the brain and with no prior exposure to an ALKi.
- Arm 5 will include any patients with leptomeningeal carcinomatosis with or without evidence of active lesion at the baseline Gadolinium-enhanced brain MRI.

Note: An active brain lesion is a lesion free of any local treatment (like stereotactic radiosurgery or whole brain radiation). The following lesions are considered active:

- A newly diagnosed brain metastasis in a patient who has never received treatment to the brain or in a patient with previously treated brain metastases.
- A brain lesion previously treated with whole brain radiation will only be considered active when there is an unequivocal size increase in its solid component (cystic component of the lesion is not considered for progression determination) compared to the first available post-radiation radiological evaluation.
- An enlarging brain lesion previously treated with SRS will only be considered active when the nature of the enlargement is clearly attributed to the tumoral component of the lesion and not to the radiation effect.

Whole body, intracranial and extracranial endpoints

Depending on the ability of ceritinib to cross the blood-brain barrier, its therapeutic activity in brain metastases may be different from its activity outside of the brain. This may affect the tumor overall response determined in a population of ALK+ NSCLC patients metastatic into the brain compared to patients without brain metastases. Whole body response and related

endpoints will be evaluated and will include the overall response rate (ORR), duration of response (DOR), disease control rate (DCR) and progression free survival (PFS) for all cancer lesions **in and outside** the brain per RECIST 1.1.

To differentially appreciate this, the intracranial activity of ceritinib **without taking into consideration lesions situated outside of the brain** will be evaluated and reported as an intracranial endpoint.

In contrast, the activity of ceritinib **outside of the brain without inclusion of brain lesions** will be evaluated and will be reported as an extracranial endpoint.

2.3 Rationale for dose and regimen selection

In the dose-escalation phase of [REDACTED], 59 patients were treated at dose levels of 50 to 750 mg. Eight Dose Limiting Toxicities (DLTs) at Cycle 1 were observed in 6 patients:

- At 400 mg: grade 3 hypophosphatemia in one patient, and grade 3 transaminase increased evolving from grade 2 ALT increased in one patient.
- At 600 mg: grade 3 diarrhea and grade 3 dehydration in one patient each.
- At 750 mg: grade 3 diarrhea with grade 3 vomiting in one patient and intolerable grade 2 diarrhea in one patient.

[REDACTED] Further confirmation of the 750 mg dose as the appropriate MTD came from the incidence of DLTs in Cycle 1 in the first 10 patients treated at this dose in the expansion phase of the study. There were no first-cycle DLTs in these 10 patients, thus confirming the 750 mg dose as a safe MTD and RD [REDACTED]

Among the different doses tested, the recommended dose (RD) for the expansion phase was determined to be 750 mg, the highest dose evaluated. The following safety and efficacy considerations were taken into account:

- Safety data indicated that ceritinib is well tolerated at 750 mg for multiple cycles of therapy, without evident difference in the frequency of AEs versus immediate lower doses (400-700 mg).
- Although preliminary efficacy data indicated that tumor responses are observed consistently at doses of 400 mg and above, the response duration appeared to be shorter at

the lower doses. Nonclinical data from ALK-positive NSCLC xenograft models indicated that ceritinib should be dosed at the MTD to maximize efficacy, in particular against crizotinib resistant tumor models.

3 Objectives and endpoints

Objectives and related endpoints are described in [Table 3-1](#) below.

[figure not shown]
[figure not shown]

[figure not shown]
Table 3-1 Objectives and related endpoints

Objective	Endpoint	Analysis
Primary		
The primary objective is to evaluate the antitumor activity of ceritinib in patients with ALK-positive NSCLC metastatic to the brain and/or to leptomeninges based on investigator assessment per RECIST 1.1	The primary endpoint is: 
 Overall response rate (ORR), defined as the proportion of patients with a best overall confirmed response of CR or PR in the whole body as assessed per RECIST 1.1 by the investigator. 	Refer to Section 10.4 .
Key Secondary Objective		
To evaluate Disease Control Rate (DCR) in patients with ALK-positive NSCLC metastatic to the brain and/or to leptomeninges based on investigator assessment per RECIST 1.1	The key secondary endpoint is: 
 Disease Control Rate (DCR) in the whole body as assessed per RECIST 1.1 by the Investigator 	Refer to Section 10.5 .
Secondary Objectives		

 To evaluate intracranial tumor-response related endpoints as assessed by investigators and Blinded Independent Review Committee (BIRC) (using modified RECIST 1.1 criteria) To evaluate extracranial tumor-response related endpoints as assessed by investigators and BIRC (using RECIST 1.1 criteria) To evaluate whole body tumor-response related endpoints as assessed by investigators and BIRC(using RECIST 1.1 criteria) To evaluate overall survival (OS) in this patient population To evaluate safety in this patient population 	
 The following intracranial endpoints will be evaluated per modified RECIST 1.1*: 
 Overall Intracranial Response Rate (OIRR) by Investigator and BIRC for patients with measurable brain metastases at baseline Intracranial Disease Control Rate (IDCR) at 8, 16 weeks and overall by Investigator and BIRC Time to intracranial tumor response (TTIR) by Investigator and BIRC for patients with measurable brain metastases at baseline Duration of intracranial response (DOIR) by Investigator and BIRC for patients with measurable brain metastases at baseline The following extracranial endpoints will be evaluated per RECIST 1.1: 
 Overall Extracranial Response Rate (OERR) by Investigator and BIRC Extracranial Disease Control Rate (EDCR) at 8, 16 weeks by Investigator and BIRC Time to extracranial tumor response (TTER) by Investigator and BIRC Duration of extracranial response (DOER) by Investigator and BIRC The following whole body tumor-response related endpoints will be evaluated per RECIST 1.1: 
 Overall response rate (ORR) by BIRC Disease control rate (DCR) by BIRC 	Refer to Section 10.5 .

Objective	Endpoint	Analysis
	
• Time to tumor response (TTR) by Investigator and BIRC• Duration of response (DOR) by Investigator by BIRC• Progression free survival (PFS) by Investigator by BIRC 
4. Overall survival (OS)
 
5. AEs, ECGs, Vital signs and laboratory abnormalities
 

	
Exploratory objectives		Refer to Section 10.6 .

1. To evaluate intracranial endpoints for patients with measurable brain metastases at baseline in Arms 1 to 4 and for patients with active brain lesions at baseline in Arms 1 to 4 using the Response Assessment in Neuro-Oncology (RANO) criteria for high grade gliomas (Wen et al 2010) by investigators and BIRC.
 

	
1. Intracranial endpoints including OIRR, Time to Intracranial Tumor Response (TTIR), Duration of Intracranial Response (DOIR) for patients with measurable brain metastases at baseline in Arms 1 to 4, and IDCR in Arms 1 to 4 for patients with active brain lesions at baseline using the Response Assessment in Neuro-Oncology (RANO) criteria for high grade gliomas (Wen et al 2010) by investigators and BIRC.
 

	

*RECIST 1.1 will be modified to allow a specific evaluation of the intracranial response to the treatment. The usual criteria to select target lesions will be used but a maximum five target lesions located in the brain can be selected at baseline and evaluated at each assessment time point.

[figure not shown]

4 Study design

4.1 Description of study design

This is a phase II, multi-center, open-label, five-arm study in which the efficacy and safety of oral ceritinib treatment for patients with ALK-positive NSCLC metastatic to the brain and/or to leptomeninges will be assessed.

[figure not shown]
[figure not shown]
Figure 4-1 Study design

[figure not shown]

Previous treatment with ALK inhibitors other than crizotinib is not allowed in Arms 1, 2 and 5.

4.1.1 Screening

All patients must harbor an ALK rearrangement as assessed using the FDA approved Vysis ALK Break Apart FISH Probe Kit (Abbott Molecular Inc.) test and scoring algorithm (including positivity criteria) **before** initiating treatment with ceritinib.

Eligibility assessment and baseline tumor burden evaluation will be conducted within 28 days prior to starting study drug except for gadolinium-enhanced brain MRI and brain specific eligibility evaluation which should be done within 14 days prior to starting study drug. See [Section 7.1.2](#) for further details.

[figure not shown]

Following completion of screening procedures and verifying patient eligibility, patients will be allocated to one of the five study arms via IRT.

- Arm 1 will include patients with metastases in the brain without evidence of leptomeningeal carcinomatosis, previously treated with radiation to the brain and with prior exposure to an ALKi.
- Arm 2 will include patients with metastases in the brain without evidence of leptomeningeal carcinomatosis, previously untreated with radiation to the brain but with prior exposure to an ALKi.
- Arm 3 will include patients with metastases in the brain without evidence of leptomeningeal carcinomatosis, previously treated with radiation to the brain but with no prior exposure to an ALKi.
- Arm 4 will include patients with metastases in the brain without evidence of leptomeningeal carcinomatosis, previously untreated with radiation to the brain and with no prior exposure to an ALKi.
- Arm 5 will include any patients with leptomeningeal carcinomatosis with or without evidence of active lesion at the baseline Gadolinium-enhanced brain MRI.

Note: Previous treatment with ALK inhibitors other than crizotinib is not allowed in Arms 1, 2 and 5

Note: An active brain lesion is a lesion free of any local treatment (like stereotactic radiosurgery or whole brain radiation). The following lesions are considered active:

- A newly diagnosed brain metastasis in a patient who has never received treatment to the brain or in a patient with previously treated brain metastases.
 - A brain lesion previously treated with whole brain radiation will only be considered active when there is an unequivocal size increase in its solid component (cystic component of the
- 

lesion is not considered for progression determination) compared to the first available post-radiation radiological evaluation.

- An enlarging brain lesion previously treated with SRS will only be considered active when the nature of the enlargement is clearly attributed to the tumoral component of the lesion and not to the radiation effect.

Approximately 160 patients will be treated in the study, ~40 patients in each Arm 1 and Arm 2, ~30 patients in each Arm 3 and Arm 4, and ~20 patients in Arm 5. Additional patients in Arm 4 may be enrolled in order to achieve ~60 patients in Arms 3 and 4 together (i.e. ALKi naïve patients) if enrollment rate in Arm 3 is slow.

Furthermore the study targets to enroll and treat the following number of patients with measurable brain metastasis at baseline as per the investigator's assessment in each of the below subgroups:

- Patients with prior ALKi treatment (combined Arms 1 and 2): ~50 patients with measurable brain metastasis
- Patients with no prior ALKi treatment (combined Arms 3 and 4): ~20 patients with measurable brain metastasis

The measurability of brain metastases will also be assessed by BIRC per RECIST 1.1 on an ongoing basis to target a similar number of patients with measurable brain metastasis at baseline as per BIRC in the above subgroups of patients. Enrollment of patients with only non-measurable brain metastases (even in the presence of extracranial measurable lesions) may be closed in one or more arms if it is determined that the above target for patients with measurable brain metastases will not be met.

4.1.2 Treatment duration

The study treatment phase begins on Cycle 1, Day 1 with the first administration of ceritinib.

All patients will receive the same treatment regimen regardless of the arm to which they are allocated. A cycle of treatment is defined as 28 days of once daily treatment of ceritinib in all study arms.

Treatment with ceritinib will continue until the patient experiences disease progression (in the brain, outside of the brain or both) as determined by the investigator according to RECIST 1.1, unacceptable toxicity that precludes further treatment, pregnancy, start of a new anticancer therapy, discontinues treatment at the discretion of the patient or investigator, lost to follow-up, death, or study is terminated by Sponsor. Exceptions to the discontinuation of study treatment after PD being confirmed by the investigator are described in [Section 6.1.3](#).

4.1.2.1 Tumor assessments during study conduct

Complete tumor assessments including gadolinium enhanced brain MRI will be repeated at Week 8 (on Cycle 3 Day 1) and every 8 weeks (i.e. every 2 cycles) thereafter or earlier if clinically indicated.

Tumor response will be evaluated starting from the first day of treatment with ceritinib until the time of disease progression according to RECIST 1.1 as determined by investigator, withdrawal of consent for further follow-up, loss to follow-up or death. This schedule of

tumor assessment must continue regardless of dose interruptions. In patients who discontinue treatment in the absence of RECIST-defined progression, tumor assessments will continue every 8 weeks until progression of disease, withdrawal of consent for further follow-up, loss to follow-up or death.

For patients presenting with baseline leptomeningeal carcinomatosis with documented malignant cells in the cerebrospinal fluid, CSF samples will be collected at a frequency determined by local clinical practice unless medically contra-indicated. Samples should be obtained from site of disease or initially positive cytology if possible. The investigator may determine if more frequent evaluations are needed in case of suspected disease progression and/or in accordance with local clinical practice. If there are any signs or radiologic or clinical neurological progression, a CSF will be collected if feasible. Clinical progression may be determined based on results of cytological or neurological evaluations.

Gadolinium-enhanced brain MRI scans and all other imaging data collected at baseline and during the conduct of the study will be submitted to the designated imaging vendor for BIRC review.

In this study, standard RECIST 1.1 will be used to evaluate the whole body (including intracranial and extracranial cancer lesions) response endpoints. Assessment of the overall response to treatment and other whole body response related endpoints will be conducted by investigators and BIRC.

Additionally, the intracranial and the extracranial metastatic disease will be evaluated as two separate entities. RECIST 1.1 and RANO for High Grade Glioma ([Wen et al 2010](#)) criteria will be used to determine intracranial tumor response based on target brain lesions, if applicable, any non-target brain lesions and any new brain lesions. RECIST 1.1 will be used to evaluate the extracranial tumor response but brain will be excluded from the evaluation.

4.1.2.2 Central radiology review of locally assessed disease progression

In case patients have equivocal disease progression according to RECIST 1.1 (in the brain, outside of the brain or both) as determined by the investigator, a confirmatory tumor assessment should be done at least 4 weeks thereafter. While the investigator is waiting for the confirmatory tumor assessment, it is preferable that the patient continue on study treatment for as long as it is clinically acceptable. However, during this time, the investigator should do whatever is medically necessary for the patient.

If the investigator does not determine disease progression, the patient should continue receiving the study drug unless there is a medical need (i.e., rapid progression or clinical deterioration) for an immediate change in therapy.

If the investigator confirms disease progression, then the patient will discontinue study drug and subsequent follow-up tumor assessments will no longer be required (except in the cases described below).

Exceptions to the discontinuation of study treatment after progressive disease (PD) being confirmed by the investigator are:

- In case of isolated brain progression with controlled disease outside of the brain, patients may continue the study drug during the treatment of the new brain lesion if appropriate. If

ceritinib has to be interrupted during the treatment of the new brain lesions, it may be resumed after the treatment of the brain lesion if:

- Brain lesions are demonstrated to be controlled by gadolinium-enhanced MRI and if patient is neurologically stable within the last 2 weeks prior to the re-initiation of study drug.
- The disease outside of the brain remains controlled prior to re-initiation of study drug. A new tumor assessment will be repeated if the last one available is older than 4 weeks.
- Time interval between last dose and re-initiation of study drug does not exceed 8 weeks.
- Patient will continue to be followed for safety and efficacy assessments as per schedule of assessment.
- If patient had PD outside of the brain (with minimally symptomatic or no PD in the brain) but still derives clinical benefit from ceritinib following investigator's judgment, patient may continue study drug and continue to be followed for safety and efficacy assessments as per schedule of assessment.

[figure not shown]
[figure not shown]
In both cases, all imaging data acquired during tumor assessments conducted after PD has been confirmed by the investigator will continue to be submitted to the designated imaging vendor who will send it to the BIRC for review.

If the patient had PD both intracranially and extracranially but still derives clinical benefit from ceritinib following investigator's judgment, patient may continue study drug and continue to be followed for safety assessments as per schedule of assessment.

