6.3.2 Treatment interruption and treatment discontinuation

If the administration of ceritinib is temporarily interrupted for reasons other than toxicity, then treatment with ceritinib may be resumed at the same dose. The same applies if the patient experiences an unacceptable toxicity not specifically described in [Table 6-3](#), provided this toxicity resolved to \leq CTCAE grade 1.

If the treatment with ceritinib is withheld due to toxicity, scheduled visits and all assessments should continue to be performed (with the exception of the dosing of the withheld study drug), as described in [Table 7-1](#).

If the treatment with ceritinib dosing is withheld for more than 28 consecutive days (counting from the first day when a dose was missed), due to treatment-related toxicity, then ceritinib should be permanently discontinued except in cases where the investigator believes the patient continues to derive clinical benefit. In such cases, treatment with ceritinib may be resumed at a lower dose. See [Section 6.1.3](#) for exception in case of isolated brain progression with controlled disease outside of the brain.

Patients whose treatment is temporarily interrupted or permanently discontinued due to a study drug related AE or an abnormal laboratory value must be followed until resolution or stabilization of the event, whichever comes first, including all study assessments appropriate to monitor the event. Detailed guidelines for follow-up of study drug related AEs or abnormal laboratory values must be followed as described in [Section 6.3.4](#).

All patients will be followed for safety until 30 days after the last dose of ceritinib. Patients whose treatment is temporarily interrupted or permanently discontinued due to an AE or abnormal laboratory value must be followed until resolution or stabilization of the event, whichever comes first, including all study assessments appropriate to monitor the event.

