6.4.1.5 Palliative radiotherapy and surgery

Local radiotherapy for analgesic purposes or for lytic lesions at risk of fracture, or for progression of the brain metastases may be carried out if required. If palliative radiotherapy is initiated after start of study treatment, the reason for its use must be clearly documented and progression as per RECIST 1.1 must be assessed and documented.

For patients with a RECIST-documented PD into the brain that are candidates to continue study drug beyond progression (see [Section 6.1.3](#) for exceptions to study drug discontinuation), as determined by the Investigator, may undergo radiotherapy and/or surgical resection as palliative localized therapy to treat metastatic lesions.

In any situation, when radiotherapy or surgery is required, ceritinib should be held for at least 4 days prior to radiotherapy and at least 1 day prior to any surgery and may be resumed ≥ 3 days after completing radiotherapy or minor surgery, and ≥ 2 weeks after major surgery.

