6.4.2 Prohibited concomitant therapy

6.4.2.1 Other anticancer therapy

Anticancer therapy (chemotherapy, targeted therapy, biologic therapy or radiation therapy (except palliative radiotherapy and palliative surgery as described in [Section 6.4.1.5](#)), and anti-cancer surgery) other than the study treatment must not be given to patients while they are enrolled in the treatment portion of the trial. If such agents are required then the patient

must be permanently discontinued from the treatment portion of the study. See [Section 6.1.3](#) for exceptions in case of isolated brain progression with controlled disease outside of the brain.

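### Section 4.1.2.2 allows ceritinib to continue while a new brain lesion is treated, which conflicts with the hold in 6.4.1.5 and the resume-after-treatment rule in 6.1.3, 7.1.4.1 and 7.2.1.3

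*Protocol*

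**What the plan says.** Protocol 4.1.2.2 lists exceptions to stopping ceritinib after investigator-confirmed progression. When only the brain has progressed, "patients may continue the study drug during the treatment of the new brain lesion if appropriate". The next sentence is conditional: if "ceritinib has to be interrupted during the treatment of the new brain lesions, it may be resumed" afterwards, provided that MRI shows the brain lesions controlled, the patient has been neurologically stable for the last 2 weeks, disease outside the brain is controlled, and no more than 8 weeks have passed since the last dose.

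Sections 6.1.3, 7.1.4.1 and 7.2.1.3 describe the same exception with the same conditions, but the only option they give is to resume after the lesion has been treated.

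Section 6.4.1.5 names radiotherapy and resection as the local treatments for patients with brain progression who stay on drug, and then states: "In any situation, when radiotherapy or surgery is required, ceritinib should be held for at least 4 days prior to radiotherapy". It adds a hold of at least 1 day before any surgery. Dosing may restart 3 or more days after radiotherapy or minor surgery, and 2 or more weeks after major surgery.

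Section 6.4.2.1 prohibits other anticancer therapy on treatment "except palliative radiotherapy and palliative surgery as described in" 6.4.1.5.

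**The concern.** The protocol gives two dosing rules for one clinical event. A site that reads 4.1.2.2 could dose through brain radiotherapy or surgery and, having interrupted nothing, would never reach the restart checks. A site that reads 6.4.1.5 or 6.1.3 would stop the drug, treat the lesion, and restart under conditions.

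What is at stake is consistent conduct and peri-procedural safety. There is also a question of classification. Protocol section 12 permits no authorised deviations, and SAP 2.4 tabulates reportable ones. Dosing through brain radiotherapy departs from 6.4.1.5 but is allowed by 4.1.2.2, so whether it counts as a deviation depends on which section is read.

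**Working it through.** There is no planned figure to reproduce. The check compares the texts, traces the cross-references and counts the doses involved.

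**1. Do the rules cover the same patients?** Yes. 4.1.2.2 concerns brain progression with continued ceritinib. 6.4.1.5 names patients with documented brain progression who are candidates to continue beyond it, and gives radiotherapy and resection as their treatment.

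**2. What does each section allow?**

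| Section | Drug during lesion treatment | Restart checks |
|---|---|---|
| 4.1.2.2 | May continue, if appropriate | Only if interrupted |
| 6.1.3 | Resumption after treatment only | Apply |
| 7.1.4.1 | Resumption after treatment only | Apply |
| 7.2.1.3 | Resumption after treatment only | Apply |
| 6.4.1.5 | Hold for radiotherapy or surgery | Gives hold times |

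Among sections stating the exception, three offer resumption only and one allows continuation.

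**3. Where are sites sent for the exception?**

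- To 6.1.3: section 4.1.2 ("Exceptions to the discontinuation of study treatment after PD being confirmed by the investigator are described in" 6.1.3), section 6.3.2 ("for exception in case of isolated brain progression with controlled disease outside of the brain"), section 6.4.1.5 ("for exceptions to study drug discontinuation") and section 6.4.2.1 ("for exceptions in case of isolated brain progression with controlled disease outside of the brain"). That is 4.
- To 4.1.2.2: section 7.1.3. That is 1.

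4.1.2.2 itself does not cite 6.4.1.5.

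**4. How many doses separate the rules?** Take a one-day procedure on day 0, once-daily dosing, no dose on the day of the procedure, and the shortest interval that 6.4.1.5 permits.

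- Radiotherapy: off from day -4 to day +2, so 4 + 1 + 2 = 7 doses.
- Minor surgery: off from day -1 to day +2, so 1 + 1 + 2 = 4 doses.
- Major surgery: off from day -1 to day +13, so 1 + 1 + 13 = 15 doses.
- 4.1.2.2 read alone: 0 doses.

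A longer radiotherapy course adds its own days. The MRI and neurological conditions in 6.1.3 could lengthen the gap further.

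**5. How many patients could a correction reach?** Amendment 6 reports 42 + 40 + 12 + 44 + 18 = 156 enrolled and 45 still on ceritinib: 45/156 = 28.8%. This is a ceiling. It counts everyone on drug, not those with locally treated isolated brain progression, whose number is not given.

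**6. Are the estimates affected?** Protocol 10.4.3 counts these patients as progressed from the time of progression, and Appendix 2 (14.2.17) leaves later assessments out of the response and disease control rates. ORR and DCR therefore do not change. SAP 4.5 derives interruptions and dose changes from the dose actually taken, so the exposure summaries reflect what happened under either rule.

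**The case against.** The best defence is that the texts can be read together. 4.1.2.2 is permissive twice over, since it says patients may continue and only if that is appropriate. Its second sentence anticipates that the drug may have to stop, and 6.4.1.5 says when. Section 6.4.2.1 allows on-treatment radiotherapy or surgery only on the terms of 6.4.1.5, so a site looking for permission for the procedure should meet the hold. The resume-only sections leave continuation out without expressly forbidding it. The word used in 6.4.1.5 is should, and a site that holds the drug breaches nothing in 4.1.2.2. Treatment of a brain lesion might also include corticosteroids, which section 6.4.1.1 permits without a hold.

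Much of this stands, and it limits the point. It does not remove it. The joint reading works only if a site sent by 7.1.3 to 4.1.2.2 also finds 6.4.1.5, which 4.1.2.2 does not mention. The corticosteroid reading is strained, because 6.4.1.5 names radiotherapy and resection as the treatments for these patients. The three resume-only sections present resumption as an exception to a general requirement to stop at confirmed progression, so an option they omit is fairly read as not allowed there.

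Two further objections are fair. The dose counts measure the gap between the texts, not any observed harm. And 6.1.3 does not cite 6.4.1.5 either, so redirecting 7.1.3 would not by itself lead a site to the hold times.

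**Conclusion.** The inconsistency is real and minor. As written, 4.1.2.2 permits dosing through brain radiotherapy or surgery, against the protocol's own hold and against the three other statements of the same exception. The gap is at least 7, 4 or 15 daily doses according to the procedure, assuming a one-day procedure and 4.1.2.2 read without 6.4.1.5. ORR and DCR are untouched. The documents give neither data on harm from concurrent use nor the number of patients concerned. With 45 of 156 patients on drug at Amendment 6, and those patients due to move to a rollover study or other access, the number who could benefit from a correction is probably well below that ceiling.

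**What to change.** In 4.1.2.2, delete the sentence allowing continuation during lesion treatment, or make it expressly subject to the 6.4.1.5 hold. Use the resumption rule and conditions of 6.1.3 for the rest of the bullet. Change the reference in 7.1.3 from 4.1.2.2 to 6.1.3, matching the other four pointers. A mention of 6.4.1.5 in 6.1.3 would also take readers to the hold times.

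The cost is one sentence and one cross-reference (two if 6.1.3 is also annotated), by amendment or site letter. No new procedure or data are needed.
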